2 STUDY DESIGN

2.1 TYPE OF STUDY

The study will consist of two sequential single arms. Patients meeting enrollment criteria will be assigned non-randomly to the study arms based on order of enrollment. Neither patients nor investigators will be blinded to the assignment. First, a dose finding arm with a standard "3 + 3" design will use venetoclax, CC-486, and obinutuzumab combination therapy in three dose levels and two optional dose de-escalation levels to establish the RP2D and assess toxicity and tolerability of the triplet. Dose-limiting toxicity will be assessed during the 28 days of Cycle 1. If a safe and tolerable RP2D is established, the study will proceed with an expansion cohort using Simon two-stage and window designs. In the expansion cohort, the first three cycles will consist of a combination of venetoclax and CC-486 before obinutuzumab is added in cycle 4. Disease assessment will take place after cycle 3 and cycle 6 and will be graded according to the Lugano Criteria (B. D. Cheson et al. 2014). Adverse events (AEs) will be monitored throughout the trial, and graded in severity according to the guidelines outlined in the NCI Common Terminology Criteria for Adverse Events (CTCAE) version 5.0. This trial will be conducted in accordance with Good Clinical Practices.

2.2 DURATION OF STUDY

The end of this study is defined as the date when the last patient, last visit (LPLV) occurs or the date at which the last data point required for statistical analysis (i.e., PET 30-month post treatment initiation) or safety follow-up is received from the last patient, whichever occurs later. The minimum

required safety follow up for all AEs is 30 days, though a subset of AEs will remain reportable indefinitely. The total duration of the study, from screening of the first patient to LPLV is expected to be 55 months or less, with an estimated 24 months to full accrual and 31 months from enrollment of the last patient to LPPV.

2.3 SCHEDULE OF EVENTS

For each study visit, basic information including body measurements and vital signs will be recorded. Symptoms of the disease and treatment-related toxicities will be collected and recorded by a licensed medical provider. A physical exam will be performed and documented by a licensed medical provider. Scheduled laboratory assessments will be drawn on the day of the appointment. The assessments and procedures conducted at each visit will follow the study schema shown in **Appendix A.**

The schedule will proceed as follows: first there will be a screening visit within 28 days prior to Cycle 1 to determine eligibility and review the protocol. A 28-day supply of venetoclax and 14-day supply of CC-486 will be given to the patient on Day 1 of each cycle. Cycle 1 will require visits on Day 1, 8, 15, and 22 for treatment, laboratory assessments, and assessment. In the dose-finding cohort only, infusional therapy with obinutuzumab will be given on Cycle 1 Day 1, Cycle 1 Day 8, and Cycle 1 Day 15 in the dose-finding arm. In the expansion cohort, no obinutuzumab will be given in Cycle 1, but the patient will be assessed for toxicity weekly.

Cycle 2 will require visits on Day 1 and Day 15. Infusional therapy with obinutuzumab will be given on Cycle 2 Day 1 in the dose-finding arm only. Cycle 3 through 12 will require visits on Day 1 only in the dose finding arm. The last dose of obinutuzumab will be given on Cycle 9 Day 1 in the dose finding arm. In the expansion cohort, obinutuzumab treatment will start in Cycle 4, with infusions and laboratory studies on Day 1, Day 8, and Day 15; subsequent Cycles through Cycle 12 will include an obinutuzumab infusion on Day 1 only. The end-of-treatment visit will occur within 4 weeks of completion of treatment on Cycle 12, Day 28. Follow-up visits will occur every 8-12 weeks until 18 months post-treatment, and every 6 months thereafter until the close of the trial or disenrollment of the patient.

2.4 SEQUENCE AND DURATION OF ALL STUDY PERIODS

Patients will undergo an initial screening phase within 28 days prior to treatment allocation. Treatment will consist of twelve 28-day cycles for a total of 336 days. Follow-up after completion of treatment will extend to the final disease response assessment at 30 months following initiation of treatment. Post-study follow-up for progression of disease, death, secondary malignancies, next treatment delivered, and late treatment-related toxicities will continue by telephone survey every 6 months until the close of the trial or disenrollment of the subject.

2.5 METHOD FOR ASSIGNING SUBJECTS TO STUDY GROUPS

Subjects will be assigned to the dose-finding arm in cohorts of 3 patients until the RP2D is established (estimated 12-18 subjects). The next 15 enrolled subjects will be assigned to the expansion cohort, stage 1. The following 17 enrolled subjects will be assigned to the expansion

cohort, stage 2. Once the expansion cohort has reached a goal of 32 total patients, further enrollment will be closed. Patients will not be randomized and will be assigned to arms, cohorts and stages by the order of enrollment alone. No placebos will be used.

2.6 BLINDING

Neither subjects nor investigators will be blinded to the investigational agents in this study.

2.7 PRIMARY STUDY ENDPOINTS

Dose-finding cohort:

- Recommended phase 2 dose, defined as the maximum tolerated dose up to dose level 3 (see Table 2)
- Rate of grade 3/4 adverse events
- Rate of discontinuation

Expansion cohort:

• Six-month complete metabolic response rate assessed by PET scan

2.8 SECONDARY STUDY ENDPOINTS

- Overall survival both at the end of the trial and as a 5-year estimate
- Progression-free survival both at the end of the trial and as a 5-year estimate
- "CR30" complete metabolic response rate at 30 months post-treatment initiation
- Three-month CR rate after 3 cycles of treatment with venetoclax and CC-486 alone (expansion cohort only)

2.9 EXPLORATORY STUDY ENDPOINTS

- Evaluation of pre-treatment tumor mutations by next generation sequencing of the tumor material for specific mutations (see Section 1.2.3.3)
- Measurement of minimal residual disease (MRD) via circulating tumor DNA
- Pharmacodynamic assessment of the effect of oral azacitidine on the circulating cell-free DNA methylation profile over time

3 SUBJECT SELECTION AND WITHDRAWAL

3.1 Number of Subjects

Twelve to eighteen subjects from any of the study sites are expected in the dose-finding arm, and 32 in the expansion cohort for a total of 44-50 patients.

3.2 GENDER, AGE, RACIAL AND ETHNIC ORIGIN OF SUBJECTS

The age of the participants in this trial will be 18 years and older. Follicular lymphoma is very rare in children and consists of a particular subtype which is biologically distinct from slow-developing adult

FL (Louissaint et al. 2016). The preclinical data supporting this trial were derived from adult FL, and do not provide adequate support for including pediatric-type nodal follicular lymphoma in this trial. Obinutuzumab has not previously been studied in a pediatric population, and there is no available safety or efficacy data for this drug in children.

Non-pregnant, non-breastfeeding women and minority populations will be included in the trial without restriction. There is inadequate safety data for the approved agents for use in pregnant and breastfeeding women, and the potential benefits of treatment. The patient population at University of Chicago Medicine is diverse in race, sex, and socioeconomic status, which will allow for generalizability of findings.

3.3 INCLUSION CRITERIA

Participants are eligible to be included in the study if all of the following criteria apply:

- 1. Male and female subjects who are at least 18 years of age with a histologic diagnosis of grade 1-3a FL by 2017 World Health Organization criteria. A prior tissue or bone marrow biopsy may be used for histologic confirmation if collected within 90 days of the initiation of therapy.
- 2. Treatment-naive or fewer than two prior lines of anti-CD20 monotherapy consisting of a total of 16 or fewer doses.
- 3. Ann Arbor Stage II-IV disease on screening PET imaging with measurable disease, defined as at least one lesion that can be accurately measured in at least two dimensions and quantifiable avidity to FDG. Minimum measurement must be >15 mm in the longest diameter by >10 mm in the short axis.
- 4. Eastern Cooperative Oncology Group (ECOG) performance status of 2 or less as defined in Appendix B. Performance status must be evaluated within 28 days prior to treatment initiation.
- 5. There must be an indication for treatment, either by meeting one or more of the GELF criteria for treatment (Brice et al. 1997), the existence of cancer-related pain or other uncontrollable symptom, or in the judgment of the primary oncologist based on pace of disease progression or other clinical criteria. Patients must have documented progression of disease.
- 6. Not be a candidate for standard-of-care chemoimmunotherapy in the judgment of the primary oncologist OR standard chemoimmunotherapy was discussed with the primary oncologist and declined by the subject.
- 7. A male participant must agree to use contraception as detailed in Appendix D of this protocol during the treatment period, and for at least 90 days after the last dose of venetoclax or 18 months after the last dose of obinutuzumab, whichever is longer, and refrain from donating sperm during this period. With pregnant female partners, men must remain abstinent or use a condom during the treatment period and for at least 6 months after the last dose of obinutuzumab to avoid exposing the embryo.

- 8. A female participant is eligible to participate if she is not pregnant (see Appendix D), not breastfeeding, and at least one of the following conditions applies:
 - a.) Not a woman of childbearing potential (WOCBP) as defined in Appendix D
 - b.) A WOCBP who agrees to follow the contraceptive guidance in Appendix D during the treatment period and for at least 30 days after the last dose of venetoclax or 18 months after the last dose of obinutuzumab, whichever is longer.
 - c.) Subjects must have a negative pregnancy test within 72 hours of beginning treatment if WOCBP.
- 9. The participant (or legally acceptable representative if applicable) provides written informed consent for the trial.
- 10. Have adequate organ function as defined in Table 1 within 28 days prior to treatment initiation.

Table 1. Adequate Organ Function Laboratory Values

Hematological	
Absolute neutrophil count	> 1500 cells per microliter unless due to bone marrow involvement
Hemoglobin	> 9 g/dL
Platelet count	> 75,000 platelets per microliter
Renal	
Creatinine clearance	> 60 mL per minute by Cockcroft-Gault equation
Hepatic	
Total bilirubin	≤ 1.5 × Upper limit of normal (ULN) OR direct bilirubin ≤ ULN for participants with total bilirubin levels > 1.5 × ULN
AST (SGOT) and ALT (SGPT)	≤2.5 × ULN, or ≤3 x ULN for patients with documented Gilbert syndrome, or ≤5 × ULN for participants with documented liver metastases

Coagulation	
International normalized ratio (INR) OR prothrombin time (PT)	≤1.5 × ULN unless participant is receiving anticoagulant therapy as long as PT or aPTT is
Activated partial thromboplastin time (aPTT)	within therapeutic range of intended use of anticoagulants

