4.2.1.2 Summary of Drug Regimen for Expansion Cohort

In the expansion cohort, the RPD2 established in the dose-finding cohort will be used. Venetoclax will be taken once daily by mouth at the RP2D every day of a 28-day cycle. CC-486 will be taken once daily by mouth at the RP2D on days 1-14 of a 28-day cycle. Obinutuzumab will be omitted from cycle 1-3. In cycle 4, obinutuzumab will be administered intravenously on days 1, 8, and 15. In cycle 5-12, obinutuzumab will be administered intravenously on day 1 only.

[figure not shown]

Figure 4: Treatment plan for expansion cohort

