8.4.2 Pregnancy in Study Subjects

If a female subject becomes pregnant (including elevated βhCG or positive pregnancy test in a female subject of reproductive potential, regardless of disease state) while receiving venetoclax, obinutuzumab and/or CC-486 or within 180 days after the last dose of venetoclax, obinutuzumab and /or CC-486, a report should be completed and expeditiously submitted to both Genentech and Celgene. The female subject should be immediately discontinued from any study therapy and should be referred to an obstetrician-gynecologist, (preferably one with reproductive toxicity experience) or another appropriate healthcare professional for further evaluation.

The Lead PI will follow the female subject until completion of the pregnancy outcome and 1 additional year after the initial report of pregnancy to ensure complete reporting of outcomes. The Lead PI must notify Celgene and Genentech Drug Safety immediately about the outcome of the pregnancy (either normal or abnormal outcome) using the Pregnancy Follow-up Report Form and Infant Follow-Up Form, or approved equivalent form.

If the outcome of a pregnancy is abnormal (e.g. spontaneous or therapeutic abortion, stillbirth, neonatal death, or congenital anomaly) in a female subject exposed to venetoclax, CC-486, and/or obinutuzumab as part of this study, the Lead PI should always report the abnormal outcome as serious, and report the event as an SAE within 24 hours of the sponsor-investigator's knowledge of the event using the appropriate SAE reporting procedures as outlined in Section 8.3.2.

All neonatal deaths that occur within 28 days of birth should be reported, without regard to causality, as SAEs. In addition, any infant death after 28 days that the Lead PI suspects is related to the in utero exposure to the study drug(s) should also be reported to Genentech and Celgene Drug Safety immediately by facsimile, or other appropriate method, within 24 hours of the Lead PI's knowledge of the event using the SAE Report Form, or approved equivalent form.

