APPENDIX D: CONTRACEPTIVE GUIDANCE AND PREGNANCY TESTING

Definition of a Woman of Childbearing Potential (WOCBP): A woman is considered fertile following menarche and until becoming post-menopausal unless permanently sterile (see below)

Women in the following categories are not considered WOCBP:

- Premenarchal
- Premenopausal female with 1 of the following:
 - Documented hysterectomy
 - Documented bilateral salpingectomy
 - Documented bilateral oophorectomy
 Note: Documentation can come from the site personnel's review of the participant's medical records, medical examination, or medical history interview.
- Postmenopausal female
 - A postmenopausal state is defined as no menses for 12 months without an alternative medical cause.
 - A high follicle stimulating hormone (FSH) level in the postmenopausal range may be used to confirm a postmenopausal state in women not using hormonal contraception or hormonal replacement therapy (HRT). However, in the absence of 12 months of amenorrhea, confirmation with two FSH measurements in the postmenopausal range is required.
 - Females on HRT and whose menopausal status is in doubt will be required to use one of the non-hormonal highly effective contraception methods if they wish to continue their HRT during the study. Otherwise, they must discontinue HRT to allow confirmation of postmenopausal status before study enrollment.

Contraception Requirements

Male Participants:

Male participants with female partners of childbearing potential are eligible to participate if they agree to one of the following during the protocol defined time frame:

- Be abstinent from penile-vaginal intercourse as their usual and preferred lifestyle (abstinent on a long term and persistent basis) and agree to remain abstinent
- Use a male condom plus partner use of a contraceptive method with a failure rate of <1% per year as described in Table 8 when having penile-vaginal intercourse with a woman of childbearing potential who is not currently pregnant.
 - Note: Men with a pregnant or breastfeeding partner must agree to remain abstinent from penile-vaginal intercourse or use a male condom during each episode of penile penetration.

Female Participants:

Female participants of childbearing potential are eligible to participate if they agree to use a highly effective method of contraception consistently and correctly as described in the below table during the protocol-defined time frame.

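### Section 3.3 conflicts with Appendix D on contraception at entry, and no visible text sets a post-treatment contraception period for CC-486

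*Combined protocol and SAP*

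**What the plan says.** **Entry logic.** Criterion 8 in section 3.3 requires that a woman be not pregnant, "not breastfeeding, and at least one of the following conditions applies". The list has three items: (a) she is not of childbearing potential; (b) she is, and agrees to the contraceptive guidance; (c) "Subjects must have a negative pregnancy test within 72 hours of beginning treatment if WOCBP". Exclusion criterion 1 in section 3.4 separately bars a woman of childbearing potential unless pregnancy is ruled out by a test in the same 72-hour frame. Appendix D states: "Female participants of childbearing potential are eligible to participate if they agree to use a highly effective method of contraception".

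**Post-treatment periods.** For women, 8(b) runs "for at least 30 days after the last dose of venetoclax or 18 months after the last dose of obinutuzumab, whichever is longer". Criterion 7 has the same form for men, with 90 days in place of 30. A further sentence in criterion 7, for men whose partner is pregnant, asks for abstinence or a condom during treatment and "for at least 6 months after the last dose of obinutuzumab to avoid exposing the embryo". Appendix D repeats the abstinence-or-condom rule for men with a pregnant or breastfeeding partner. It gives no durations of its own and refers back to the time frame set by the protocol.

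**Exposure and reporting.** In the expansion cohort (section 4.2.1.2), "Obinutuzumab will be omitted from cycle 1-3". Section 8.4.2 makes a pregnancy reportable during treatment or "within 180 days after the last dose of venetoclax, obinutuzumab and /or CC-486". Section 8.4.3 applies the same 180 days to partners of male patients.

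**The concern.** Criterion 8 is an eligibility rule that a site may apply as a checklist. Applied literally, it can give a different answer from Appendix D about whether a woman of childbearing potential must agree to contraception before she starts three study drugs.

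The post-treatment wording names two of those drugs. CC-486 is covered while treatment lasts, but nothing visible says what applies afterwards. The gap is most exposed in the expansion cohort's three-cycle window. Stopping there is a route the design itself provides: a PET scan is due before Cycle 4 Day 1 (section 5.5.2), and confirmed radiographic progression requires discontinuation (section 3.12). A patient who leaves then has had only venetoclax and CC-486, so the 18-month obinutuzumab limb has no starting date.

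At stake is a participant-protection rule that sites could read in different ways. No estimate, error rate or sample size depends on it.

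**Working it through.** **Step 1: criterion 8 beside exclusion 1 and Appendix D.** Take a woman of childbearing potential who declines contraception and has a negative test.

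- Criterion 8: (a) fails, (b) fails, (c) is met. One item is enough, so she passes.
- Exclusion 1: negative test, so she is not excluded.
- Appendix D: no agreement, so its condition is not met.

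Every such woman who clears exclusion 1 also meets (c). Within section 3.3, (b) therefore never decides a case, and the agreement rests on Appendix D alone.

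**Step 2: which drugs carry a post-treatment period.**

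| Text | Venetoclax | Obinutuzumab | CC-486 |
|---|---|---|---|
| Criterion 8(b), women | 30 days | 18 months | none |
| Criterion 7, men | 90 days | 18 months | none |
| Criterion 7, pregnant partner | none | 6 months | none |
| Appendix D | refers back | refers back | refers back |
| 8.4.2 and 8.4.3, reporting | 180 days | 180 days | 180 days |

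**Step 3: expansion patient who stops at the end of cycle 3.** Cycles are 28 days. Venetoclax is taken daily and CC-486 on days 1-14 (section 4.2.1.2).

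- Last venetoclax: 3 × 28 = Day 84. Last CC-486: 2 × 28 + 14 = Day 70.
- Contraception duty ends: women 84 + 30 = Day 114; men 84 + 90 = Day 174.
- Reporting ends: 84 + 180 = Day 264 from venetoclax; 70 + 180 = Day 250 from CC-486.
- Difference from venetoclax: 264 − 114 = 150 days (women); 264 − 174 = 90 days (men).
- Difference from CC-486: 250 − 114 = 136 days (women); 250 − 174 = 76 days (men).

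For contrast, one obinutuzumab dose on Cycle 4 Day 1 (Day 85), with 18 months taken as about 548 days, moves the end of the duty for both sexes to about 85 + 548 = Day 633.

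**Step 4: reduced venetoclax schedule.** Table 4 allows venetoclax on days 1-10 only, so CC-486 (to day 14) becomes the last drug taken in the cycle. The duty then ends 10 + 30 − 14 = 26 days (women) or 10 + 90 − 14 = 86 days (men) after the last CC-486 dose.

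**Step 5: pregnant-partner sentence.** It counts from obinutuzumab only, so a man who never receives obinutuzumab has no date to count from. If Appendix D's pregnant-partner note carries over criterion 7's main window, such a man has 90 days after venetoclax. A man who did receive obinutuzumab then has 18 months from one sentence of criterion 7 and 6 months from the next.

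**The case against.** **On criterion 8.** Item (c) is worded as an obligation and looks like a required test misplaced in an either/or list. Appendix D independently requires the agreement. A reader might infer that the protocol as a whole admits women without contraception. It does not: the fault is a conflict between section 3.3 and Appendix D, most likely a drafting slip. The list still gives the wrong answer when applied as written.

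**On the 180 days.** A reader might take this as the plan's own exposure period and conclude that early stoppers are released 150 or 90 days too soon. The documents do not support that. Sections 8.4.2 and 8.4.3 define when a pregnancy must be reported. Section 8.2.6 refers to possible fetal exposure, but it too is a reporting trigger. The 180 days apply alike to drugs for which the contraception periods differ, and after obinutuzumab the contraception period is the longer one, by about 548 − 180 = 368 days. A reporting window longer than a contraception window is not in itself a contradiction. Whether 30 or 90 days is adequate cannot be judged from these documents.

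**On pregnant partners.** Read alone, the 6-month sentence seems to leave dose-finding men short. Last obinutuzumab is 8 × 28 + 1 = Day 225, and 225 + 183 = Day 408. That is 18 days before 336 + 90 = Day 426, the end of the 90-day venetoclax period. But if Appendix D's note brings in the main window, these men are covered to about 225 + 548 = Day 773, and no shortfall arises. On the same reading, a man whose obinutuzumab stopped at Cycle 1 Day 1 would be covered to about 1 + 548 = Day 549, well past Day 336, so protection would not end with treatment. What stands is an inconsistency between the texts.

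**On what can be seen.** The consent form was not available for this review and may address CC-486.

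**Conclusion.** The concern holds in three limited parts.

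1. Criterion 8 makes a negative test sufficient within section 3.3 and so conflicts with Appendix D.
2. No visible text ties a post-treatment contraception period to CC-486. Expansion patients who stop in cycles 1-3 are left with the venetoclax limb alone. Dose-finding patients receive obinutuzumab from Cycle 1 Day 1, so this consequence does not arise for them.
3. The pregnant-partner sentence has no anchor for men who never receive obinutuzumab, and it may contradict the main window of its own criterion.

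The mismatch with the reporting window is 150 days (women) or 90 days (men) counted from venetoclax, and 136 or 76 days counted from CC-486. The CC-486 figures assume full dosing through the end of cycle 3; the venetoclax figures are simply 180 − 30 and 180 − 90. They measure disagreement between two windows, not a proven safety shortfall. The number of patients affected is probably small, but the documents give no figure for stops before cycle 4. The point should be settled because it concerns a safety-related entry rule and the correction is simple.

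**What to change.** Correct the joining logic of criterion 8 so that it agrees with Appendix D and exclusion criterion 1. Reconcile criteria 7 and 8(b), the pregnant-partner sentence, Appendix D and sections 8.4.2-8.4.3, so that the plan states a position for each study drug a patient actually received, CC-486 included, and for patients who never reach obinutuzumab. The sponsor should take the durations from its own safety documents; none is proposed here.

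The cost is wording in section 3.3, Appendix D and the consent form, with no effect on sample size, power or analysis. The possible downside is a longer contraceptive commitment for the few patients who stop early.
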